11.7.2. Handling of Missing Data

Element	Reporting Detail
General	Missing data occurs when any requested data is not provided, leading to blank fields on the collection instrument :
	 These data will be indicated by the use of a "blank" in subject listing displays. Unless all data for a specific visit are missing in which case the data is excluded from the table.
	 Answers such as "Not applicable" and "Not evaluable" are not considered to be missing data and should be displayed as such.
Outliers	Any subjects excluded from the summaries and/or statistical analyses will be documented along with the reason for exclusion in the clinical study report.

11.7.2.1. Handling of Missing Dates

Element	Reporting Detail
General	Partial dates will be displayed as captured in subject listing displays.

11.7.2.2. Handling of Partial Dates

Element	Reporting Detail
Concomitant Medications	 Partial dates for any concomitant medications recorded in the CRF will not be imputed.
	The recorded partial date will be displayed in listings.
Adverse Events, Exposure	 No missing data is expected for AE and EX. Data Management will query any missing date of AE or EX.

11.7.2.3. Handling of Missing Data for Statistical Analysis

Element	Reporting Detail
Time to Clinical Resolution	 For the primary analysis, a Discontinuation=Failure approach will be used (see Section 7.1.2). This approach handles two types of missing data: due to subjects who prematurely discontinued the study sporadic missing vital sign assessments

11.8. Appendix 8: Values of Potential Clinical Importance

11.8.1. Laboratory Values

Laboratory parameter will be graded according to the Division of AIDS (DAIDS) toxicity scales (protocol Section 12.5).

11.8.2. ECG

The following subdivision will be used to summarize the absolute and increase from baseline QTc interval data, and absolute PR interval by category

ECG Parameter	Potential Clinical Importance Range (PCI)	Unit
Absolute QTc Interval	>450 to ≤480	msec
Absolute QTc Interval	>480 to ≤500	msec
Absolute QTc Interval	>500	msec
Increase from Baseline QTc	>30 to ≤60	msec
Increase from Baseline QTc	>60	msec
Absolute PR interval	210-250	msec
Absolute PR interval	>250	msec

11.8.3. Vital Signs

Due to patient population, vital signs will not be flagged as potential clinical importance.

11.9. Appendix 9: Examination of Covariates, Subgroups & Other Strata

11.9.1. Examination of Covariates, Subgroups & Other Strata

Given the small number of subjects, no subgroups will be assessed.

11.10. Appendix 10: Multiple Comparisons & Multiplicity

11.10.1. Handling of Multiple Comparisons & Multiplicity

There will be no adjustments for multiplicity.

11.11. Appendix 11: Model Checking and Diagnostics for Statistical Analyses

11.11.1. Statistical Analysis Assumptions

Not applicable

11.12. Appendix 12 – Abbreviations & Trade Marks

11.12.1. Abbreviations

11.12.2. Trademarks

Trademarks of the GlaxoSmithKline Group of Companies

RELENZA

Trademarks not owned by the GlaxoSmithKline Group of Companies
Captisol
FluPRO
KATZ ADL
SAS
Tamiflu

11.13. Appendix 13: List of Data Displays

11.13.1. Data Display Numbering

The following numbering will be applied for RAP generated displays:

Section	Tables	Figures
Study Population	1.1 to 1.n	1.1 to 1.n
Efficacy	2.1 to 2.n	2.1 to 2.n
Safety	3.1 to 3.n	3.1 to 3.n
Pharmacokinetic	4.1 to 4.n	4.1 to 4.n
Biomarker	5.1 to 5.n	5.1 to 5.n
Pharmacodynamic / Biomarker	6.1 to 6.n	6.1 to 6.n
Pharmacokinetic / Pharmacodynamic	7.1 to 7.n	7.1 to 7.n
Health Outcome	8.1 to 8.n	8.1 to 8.n
Virology	9.1 to 9.n	9.1 to 9.n
Section	List	ings
ICH Listings	1 t	0 X
Other Listings	y t	0 Z

11.13.2. Mock Example Shell Referencing

Non IDSL specifications will be referenced as indicated and if required an example mock-up displays provided in Appendix 14: Example Mock Shells for Data Displays.

Section	Figure	Table	Listing
Study Population	POP_Fn	POP_Tn	POP_Ln
Efficacy	EFF_Fn	EFF_Tn	EFF_Ln
Safety	SAFE_Fn	SAFE_Tn	SAFE_Ln
Pharmacokinetic	PK_Fn	PK_Tn	PK_Ln
Biomarker	BM_Fn	BM_Tn	BM_Ln
Pharmacodynamic / Biomarker	BMPD_Fn	BMPD_Tn	BMPD_Ln
Pharmacokinetic / Pharmacodynamic	PKPD_Fn	PKPD_Tn	PK/PD_Ln
Health Outcomes	HO_Fn	HO_Tn	HO_Ln
Virology	VR_Fn	VR_Tn	VR_Ln

NOTES:

 Non-Standard displays are indicated in the 'IDSL / TST ID / Example Shell' or 'Programming Notes' column as '[Non-Standard] + Reference.'

11.13.3. Deliverable [Priority]

Delivery [Priority] [1]	Description
DL	Data Look (blinded dry run)
IA	Interim Analysis Statistical Analysis Complete
HL	Headline
SAC	Final Statistical Analysis Complete

NOTES:

^{1.} Indicates priority (i.e. order) in which displays will be generated for the reporting effort.

11.13.4. Study Population Tables

Study I	Study Population Tables					
No.	Population	IDSL / TST ID / Example Shell	Title	Programming Notes		
Subjec	t Disposition					
1.1.	ITT-E	ES1	Summary of Subject Disposition			
1.2.	ITT-E	SD4	Summary of Treatment Status and Reasons for Discontinuation of Study Treatment			
Protoc	ol Deviation					
1.3.	ITT-E	DV1	Summary of Important Protocol Deviations			
Popula	tion Analysed					
1.4.	All Subjects Screened	SP1	Summary of Study Populations			
Demog	raphic and Bas	eline Characteris	tics			
1.5.	ITT-E	DM1	Summary of Demographic Characteristics	Add age groups <35, 35-<50, >=50 and < 65, >=65. Add BMI and BMI categories <=20, 20-<=25, 25- <=30, 30-<=35, 40-<=45,>45. Add tobacco use.		
1.6.	ITT-E	DM5	Summary of Race and Racial Combinations			
Prior a	Prior and Concomitant Medications					
1.7.	ITT-E	POP T2	Summary of Prior Exposure to Oseltamivir	Add a footnote "Only influenza therapies taken within 7 days of baseline visit were collected" CMPRIOR='Y" or if medication started prior to IP start.No imputation for missing values		

Study F	Study Population Tables					
No.	Population	IDSL / TST ID / Example Shell	Title	Programming Notes		
1.8.	ITT-E	CM1	Summary of Prior Anti-influenzaTherapy	Includes pre-treatment CMs used for Anti-influenza therapy. Study team to review & provide list of CM terms prior to DBR Add a footnote "Only influenza therapies taken within 7 days of baseline visit were collected"		
1.9.	ITT-E	CM1	Summary of Post-Treatment Anti-influenzaTherapy	Consider post-treatment as those records where the conmed start or end date are after the IP end date. Apply same logic for Table 1.11		
1.10.	ITT-E	CM1	Summary of Pre-Treatment Steroids Use by Duration of Time	Add a column for "Pre-Treatment Steriod Use' Add a footnote "Only influenza therapies taken within 7 days of baseline visit were collected" the steroid use will be grouped as 3 categories, <1 week, 1 week – <6 months and 6 months and more, the table will summarize the number and percent of subject in each group		
1.11.	ITT-E	CM1	Summary of Post-Treatment Steroid Use			
Other						
1.12.	ITT-E	POP T3	Summary of Flu Type and Symptoms	Includes influenza subtypes		
1.13.	ITT-E	MH4	Summary of Past and Current Medical Conditions	By 'Past', 'Current', 'No'		
1.14.	ITT-E	POP T4	Summary of Ventilation Status at Baseline			
1.15.	ITT-E	POP T6	Summary of Exposure to Study Treatment			
1.16.	IPP	POP T4	Summary of Ventilation Status at Baseline			

11.13.5. Efficacy Tables

Efficacy Tables					
No.	Population	IDSL / TST ID / Example Shell	Title	Programming Notes	
Efficacy					
2.1.	IPP	EFF T2	Summary of Improved Clinical Response		
2.2.	IPP	EFF T6	Summary of Improved Respiratory Response		
2.3.	IPP		Summary of Post Baseline Ventilation Status	Mock per IVZ	
2.4.	IPP	CM1	Summary of Frequency of Associated Antibiotic Use for Treatment of Complications of Influenza	List will be identified by study team prior to unblinding	

11.13.6. Efficacy Figures

No.	Population	IDSL / TST ID / Example Shell	Title	Programming Notes
2.1.	IPP	EFF F1	Individual Plot of Time to Clinical Response	10 lines for 10 subjects with different symbols representing event or censoring and different color representing different treatment.

CONFIDENTIAL

No.	Population	IDSL / TST ID / Example Shell	Title	Programming Notes
2.2.	IPP	EFF F1	Individual of Time to Respiratory Response (Improved Respiratory Status)	10 lines for 10 subjects with different symbols representing event or censoring and different color representing different treatment, including any subject who resolved prior to baseline (negative response time, with a footnote).

11.13.7. Safety Tables

No.	Population	IDSL / TST ID / Example Shell	Title	Programming Notes
3.1.	Safety	SAFE T1	Summary of All Adverse Events by System Organ Class and Maximum Grade	Please add a footnote to indicate "Mild or Grade 1", "Moderate or Grade 2", "Severe or Grade 3", "Grade 4".
3.2.	Safety	AE3	Summary of All Adverse Events by Overall Frequency	
3.3.	Safety	AE3	Summary of Grade 2-4 Adverse Events by Overall Frequency	
3.4.	Safety	AE3	Summary All Drug-Related Adverse Events by Overall Frequency	
3.5.	Safety	AE1	All Non-Serious Adverse Events by SOC and PT	Eudra
3.6.	Safety	AE16	SAE with number of subjects and number of occurrences by SOC and PT	Eudra
3.7.	Safety	AE3	Summary of Drug-Related Grade 2-4 Adverse Events by Overall Frequency	
3.8.	Safety	AE3	Summary of Adverse Events of Special Interest by Overall Frequency	AE terms for AESI will be provided prior to unblinding.
3.9.	Safety	AE8	Listing of Adverse Events for Subjects with Neutropenia (>= Grade 1)	
3.10). Safety	AE3	Summary of Non-Fatal Serious Adverse Events	

No.	Population	IDSL / TST ID / Example Shell	Title	Programming Notes
3.1	1. Safety	AE1	Summary of Serious Adverse Events by System Organ Class	
3.1	2. Safety	AE1	Summary of Drug-Related Serious Adverse Events by System Organ Class	
3.1	3. Safety	AE3	Summary of Drug-Related Non-Fatal Serious Adverse Events	
3.1	4. Safety	AE15	Summary of Non-serious Adverse Events by System Organ Class and Preferred Term (Number of Subjects and Occurrences)	
3.1	5. Safety		Summary of Maximum Treatment Emergent Toxicities of All Lab Parameters	IDMC output
3.1	6. Safety	SAFE T2	Summary of Data Supporting Safety Halting Criteria	
3.1	7. Safety	LB1	Summary of Creatinine by Visit	
3.1	Safety 8.	LB1	Summary of Change from Baseline for Serum WBCs, % Neutrophils, and Absolute Neutrophils Counts, Creatinine, Liver Function Test	IDMC output
3.1	9. Safety	LB1	Summary of Absolute Neutrophils Count by Visit	

11.13.8. Safety Figures

No.	Population	IDSL / TST ID / Example Shell	Title	Programming Notes
3.1.	Safety		Individual Plot of Creatinine by Visit by Subject	
3.2.	Safety		Individual Plot of Absolute Neutrophils Count by Visit by Subject	Page per each subject with a vertical line on day of treatment discontinued, include treatment, sex, age, in addition to subject ID

11.13.9. Pharmacokinetic Tables

No.	Population	IDSL / TST ID / Example Shell	Title	Programming Notes
4.3	PK	PK06	Summary of Derived Whole Blood Danirixin PK Parameters (non-transformed and log-transformed) by Treatment	
4.4	PK	PK01	Summary of Whole Blood Danirixin Pharmacokinetic Concentration-Time Data (insert units) by Treatment and Day	Replace (insert units) with unit of measure. Include all subjects

11.13.10. Pharmacokinetic Figures

No.	Population	IDSL / TST ID / Example Shell	Title	Programming Notes
4.1	PK	PK20	Median (IR) Plot of Whole Blood Danirixin Concentration- Time Plot (Linear and Semi-Log) by Treatment	Include line for LLQ along with footnote defining LLQ value Overlay Day 1, 3 and 5.
4.2	PK	PK20	Mean (SE) Plot of Whole Blood Danirixin Concentration- Time Plot (Linear and Semi-Log) by Treatment	Include line for LLQ along with footnote defining LLQ value Overlay Day 1, 3 and 5.
4.5	PK	PK16a	Individual Whole Blood Danirixin Concentration-Time Plots by Subject (Linear and Semi-log)	1. X-axis displays actual relative time 2. Include line for LLQ along with footnote defining LLQ value 3. Include values below LLQ 4. Overlay Day 1, 3 and 5

11.13.11. Biomarker Figures

No.	Population	IDSL / TST ID / Example Shell	Title	Programming Notes
5.1.	IPP	BM_F2	Individual Plot of Serum Biomarkers by Visit by Subject - Influenza Positive Population	spaghetti plot, one plot per biomarker per matrix. Subject ID and treatment group should be identifiable by color/symbol
5.2.	IPP	BM_F2	Individual Plot of Nasal Wash Biomarkers by Visit by Subject - Influenza Positive Population	spaghetti plot, one plot per biomarker. Subject ID and treatment group should be identifiable by color/symbol

CONFIDENTIAL

No.	Population	IDSL / TST ID / Example Shell	Title	Programming Notes
5.3.	IPP	BM_F2	Individual Plot of Nasal SAM Strips Biomarkers by Visit by Subject - Influenza Positive Population	spaghetti plot, one plot per biomarker. Subject ID and treatment group should be identifiable by color/symbol
5.4.	IPP	BM_F2	Individual Plot of BAL Biomarkers by Visit by Subject - Influenza Positive Population	spaghetti plot, one plot per biomarker. Subject ID and treatment group should be identifiable by color/symbol

11.13.12. Pharmacodynamic / Biomarker Figures

No.	Population	IDSL / TST ID / Example Shell	Title	Programming Notes
6.1.	IPP	BMPD_F3	Matrix Comparative Plot of Individual Scatter Plot of Biomarkers vs Biomarkers for Each Biomarker Source by Select Visits	One page per biomarker. The x on y axis will contain the 5 biomarkers: Serum, Nasal wash, Nasal SAM Strips, BAL Include the pearson's correlation coefficient and p-value on the graph. Use one color One page for Day 1, Day 5, Day 45, PT Day 3
6.2.	IPP	BMPD_F1	Individual Scatter Plot of Area Under the Curve Serum Biomarkers vs. Time to Clinical Response - Influenza Positive Population	One page per biomarker. TTCR on y axis, AUC biomarker on x axis. AUC(0-5) vs TTCR, AUC(0-45) vs TTCR, AUC(0-PT Day 3) vs TTCR, Different color for treatment. Include a regression line for each treatment group
6.3.	IPP	BMPD_F1	Individual Scatter Plot of Area Under the Curve Serum Biomarkers vs. Time to Respiratory Response - Influenza Positive Population	One page per biomarker. TTRR on y axis, AUC biomarker on x axis. AUC(0-5) vs TTRR, AUC(0-45) vs TTRR, AUC(0-PT Day 3) vs TTRR, Different color for treatment. Include a regression line for each treatment group
6.4.	IPP	BMPD_F1	Individual Scatter Plot of Area Under the Curve Nasal Wash Biomarkers vs. Time to Clinical Response - Influenza Positive Population	One page per biomarker. TTCR on y axis, AUC biomarker on x axis. AUC(0-5) vs TTCR, AUC(0-45) vs TTCR, AUC(0-PT Day 3) vs TTCR, Different color for treatment. Include a regression line for each treatment group

No.	Population	IDSL / TST ID / Example Shell	Title	Programming Notes
6.5.	IPP	BMPD_F1	Individual Scatter Plot of Area Under the Curve Nasal Wash Biomarkers vs. Time to Respiratory Response - Influenza Positive Population	One page per biomarker. TTRR on y axis, AUC biomarker on x axis. AUC(0-5) vs TTRR, AUC(0-45) vs TTRR, AUC(0-PT Day 3) vs TTRR, Different color for treatment. Include a regression line for each treatment group
6.6.	IPP	BMPD_F1	Individual Scatter Plot of Area Under the Curve Nasal SAM Strips Biomarkers vs. Time to Clinical Response - Influenza Positive Population	One page per biomarker. TTCR on y axis, AUC biomarker on x axis. AUC(0-5) vs TTCR, AUC(0-45) vs TTCR, AUC(0-PT Day 3) vs TTCR, Different color for treatment. Include a regression line for each treatment group
6.7.	IPP	BMPD_F1	Individual Scatter Plot of Area Under the Curve Nasal SAM Strips Biomarkers vs. Time to Respiratory Response - Influenza Positive Population	One page per biomarker. TTRR on y axis, AUC biomarker on x axis. AUC(0-5) vs TTRR, AUC(0-45) vs TTRR, AUC(0-PT Day 3) vs TTRR, Different color for treatment. Include a regression line for each treatment group
6.8.	IPP	BMPD_F1	Individual Scatter Plot of Area Under the Curve BAL Biomarkers vs. Time to Clinical Response - Influenza Positive Population	One page per biomarker. TTCR on y axis, AUC biomarker on x axis. AUC(0-5) vs TTCR, AUC(0-45) vs TTCR, AUC(0-PT Day 3) vs TTCR, Different color for treatment. Include a regression line for each treatment group
6.9.	IPP	BMPD_F1	Individual Scatter Plot of Area Under the Curve BAL Biomarkers vs. Time to Respiratory Response - Influenza Positive Population	One page per biomarker. TTRR on y axis, AUC biomarker on x axis. AUC(0-5) vs TTRR, AUC(0-45) vs TTRR, AUC(0-PT Day 3) vs TTRR, Different color for treatment. Include a regression line for each treatment group

11.13.13. Pharmacokinetic / Pharmacodynamic Tables

Not Applicable

11.13.14. Pharmacokinetic / Pharmacodynamic Figures

No.	Population	IDSL / TST ID / Example Shell	Title	Programming Notes
7.12	IPP		Target Engagement Biomarker versus DNX PK Parameters	Target engagement biomarkers include IL-8, MPO, neutrophil elastase and neutrophil counts (the one from nasal wash, not the one from blood)

11.13.15. Health Outcome Tables

No.	Populatio n	IDSL / TST ID / Example Shell	Title	Programming Notes
8.1.	IPP	HO T2	Summary of Change from Baseline in KATZ ADL Score and each ADL Activity	Includes baseline value
8.2.	IPP	HO T5	Summary of FLU-PRO Total and Domain Scores	Use "Baseline" for label instead of "Baseline for CFB"
8.3.	IPP	HO T5	Summary of Change from Baseline FLU-PRO Total and Domain Scores	Includes baseline value

11.13.16. Virology Tables

No.	Populatio n	IDSL / TST ID / Example Shell	Title	Programming Notes
9.1.	IPP	VR T1	Summary of Change from Baseline in Influenza Viral Load by qRT-PCR (log 10 VP/mL) Overall	Includes baseline value Summarize by A and B combined
9.2.	IPP	VR T2	Summary of Change from Baseline in Influenza Viral Load by qVC (log10 TCID50/mL) for Subjects Culture Positive at Baseline –Nasopharyngeal	Includes baseline value
9.3.	ITTE	VR T7	Proportion of Subjects with Other Co-infected Viruses by Multiplex RT PCR.	
9.4.	IPP	VR T4	Summary of Resistance Associated Mutations Detected in the NA Gene by Subtype - Nasopharyngeal	
9.5.	IPP	VR T4	Summary of Resistance Associated Mutations Detected in the HA Gene by Subtype - Nasopharyngeal	

11.13.17. Virology Figures

No.	Populatio n	IDSL / TST ID / Example Shell	Title	Programming Notes
9.1.	IPP	VR F1	Individual Plot of Change from Baseline in Influenza Viral Load by qRT-PCR (log10 VP/mL) by Subject for Influenza A and B - Nasopharyngeal	Include zero at baseline
9.2.	IPP	VR F1	Individual Plot of Change from Baseline in Influenza Viral Load by qVC (log10 TCID50/mL) for Subjects Culture Positive at Baseline -Nasopharyngeal	Include zero at baseline

11.13.18. ICH Listings

ICH : Li	ICH : Listings						
No.	Population	IDSL / TST ID / Example Shell	Title	Programming Notes			
Subjec	Disposition						
1.	All Subjects Screened	ES7	Listing of Screen Reasons for Screen Failure				
2.	ITT-E	ES2	Listing of Reasons for Study Withdrawal				
3.	ITT-E	SD2	Listing of Reasons for Study Treatment Discontinuation				
4.	ITT-E	BL1	Listing of Subjects for Whom the Treatment Blind was Broken				
5.	ITT-E	TA1	Listing of Planned and Actual Treatments				
Protoco	ol Deviations						
6.	ITT-E	DV2	Listing of Important Protocol Deviations				
7.	ITT-E	IE3	Listing of Subjects with Inclusion/Exclusion Criteria Deviations				
Popula	tions Analysed						
8.	All Subjects Screened	SA3a	Listing of Subjects Excluded from Any Population				
Demog	Demographic and Baseline Characteristics						
9.	ITT-E	DM2	Listing of Demographic Characteristics				
10.	ITT-E	DM9	Listing of Race				

ICH : Li	ICH : Listings						
No.	Population	IDSL / TST ID / Example Shell	Title	Programming Notes			
11.	ITT-E	CM2	Listing of Concomitant Medications	Add column to indicate 'complications of influenza'			
12.	ITT-E	MH2	Listing of Past and Current Medical Conditions				
13.	ITT-E	MH2	Listing of Subjects with Renal Impairment	Renal impairment is based on Creatinine Clearance Criteria Any time during study including baseline and post baseline			
14.	IIT-E	CM2	Listing of Subjects with Prior Oseltamivir Exposure				
Exposu	re and Treatme	ent Compliance					
15.	Safety	EX3	Listing of Exposure Data				
Advers	e Events						
16.	Safety	AE8	Listing of All Adverse Events	Add asterisk for subjects with baseline renal impairment			
17.	Safety	AE2	Listing of Relationship Between Adverse Event System Organ Classes, Preferred Terms, and Verbatim Text				
18.	Safety	AE8	Listing of Adverse Events of Special Interest				
Serious	and Other Sig	nificant Adverse l	Events				
19.	Safety	AE8	Listing of Fatal Adverse Events				
20.	Safety	AE8	Listing of Non-Fatal Serious Adverse Events				
21.	Safety	SAFE L1	Listing of Reasons for Considering as a Serious Adverse Event	Use study 201682 as a reference			

ICH : Li	ICH : Listings						
No.	Population	IDSL / TST ID / Example Shell	Title	Programming Notes			
22.	Safety	AE8	Listing of Adverse Events Leading to Withdrawal from Study				
23.	Safety	AE8	Listing of Adverse Events Leading to Permanent Discontinuation of Study Treatment`				
24.	Safety	MH2	Listing of Subjects with Liver Stopping Events				
All Lab	oratory						
25.	Safety	LB5	Listing of Laboratory Data for Subjects with Abnormalities of Potential Clinical Concern (Grade 3-4)				
26.	Safety	LB5	Listing of All Laboratory Data				
ECG							
27.	Safety	CP_EG3	Listing of All ECG Values for Subjects with a Value of Potential Clinical Importance				
28.	Safety	CP_EG5	Listing of Abnormal ECG Findings				

11.13.19. Non-ICH Listings

Non-ICH: Listings							
No.	Population	IDSL / TST ID / Example Shell	Title	Programming Notes	Need for early terminated study		
Popula	ition						
29.	ITT-E	POP L1	Listing of Flu Type and Symptoms				
30.	ITT-E	POP L2	Listing of Chest X-Ray Results	Indicate if subject is included	d in IPP		
Efficacy	у						
31.	IPP	EFF L1	Listing of Time to Clinical Response				
32.	IPP	EFF L2	Listing of Time to Respiratory Response				
33.	IPP		Listing of Vital Signs				
34.	IPP		Listing of Ventilation Status – Mechanical Ventilation	Use NAI114373 as a refer Add start and stop time			
35.	IPP		Listing of Ventilation Status – Supplemental Oxygen	Use NAI114373 as a refer Oxygen saturation history should be inc			
36.	IPP		Listing of Hospital Discharge	Include date, duration and r	reason		
37.	IPP		Listing of Subjects Who Were Admitted to Intensive Care Unit				
Safety	Safety						
38.	Safety	LB5	Listing of Absolute Neutrophils for Subjects with Grade 3-4 Absolute Neutrophils or AE of Neutropenia				
39.	Safety	LB5	Listing of Creatinine for Subjects with Creatinine Increase > 0.5 mg/dl in Two Consecutive Visits				

Non-IC	H : Listings				
No.	Population	IDSL / TST ID / Example Shell	Title	Programming Notes	Need for early terminated study
PK					
40.	PK	PK L1	Listing of Whole Blood Danirixin Pharmacokinetic Concentration Data	Include NQ values	
41.	PK	LPK2	Listing of Whole Blood Danirixin Derived Pharmacokinetic Parameters		
Biomar	ker				
42.	ITT-E		Listing of Serum Biomarkers		
43.	ITT-E		Listing of Nasal Wash Biomarkers		
44.	ITT-E		Listing of Nasal SAM Strips Biomarkers		
45.	ITT-E		Listing of BAL Biomarker		
Virolog	У				
46.	ITT-E	VR L1	Listing of Influenza Viral RNA (qRT-PCR and TCID50) in Nasopharyngeal	Use study 201682 as a refe	erence
47.	IPP	VR L2	Listing of Co-infected Subjects		
48.	ITT-E		Listing of Other Viruses by Multiplex RT PCR.		
49.	ITT-E		Listing of Phenotypic IC50 Results	Use NAI114373 as a refer	ence
50.	IPP		Listing of Resistant Mutations in NA and HA Genes	Use NAI114373 as a refer	ence
Health	Outcome			,	
51.	IPP	HO L1	Listing of Hospital Readmission		
52.	IPP	HO L2	Listing of ADL KATZ Score and each ADL Activity		
53.	IPP	HO L3	Listing of 3-Point Scale (Bed Rest, Limit Ambulation, Unrestricted)		

Non-ICH: Listings					
No.	Population	IDSL / TST ID / Example Shell	Title	Programming Notes	Need for early terminated study
54.	IPP	HO L4	Listing of FLU-PRO Total and Domain Scores		

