9.4.2. Safety Analysis

All safety analyses will be based on the Safety Population defined in Section 9.3.1.

Exposure to study medication, measured by the number of days on study drug, will be summarized by treatment arm. The proportion of subjects reporting adverse events (AEs) will be tabulated for each treatment arm. The following summaries of AEs will be provided:

Incidence and severity of All AEs;

Incidence and severity of treatment related AEs;

Incidence and severity of AEs leading to withdrawal from study;

Incidence of serious AEs (SAEs).

Laboratory data, vital signs and ECG data (absolute values and change from Baseline) will be summarized by visit and treatment group. In addition, the maximum post-baseline toxicity grade will be tabulated by treatment.

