2. SUMMARY OF KEY PROTOCOL INFORMATION

2.1. Changes to the Protocol Defined Statistical Analysis Plan

Given that the study has been terminated early and only 10 subjects have been enrolled, no formal hypothesis testing will be performed for the study. All analyses will be descriptive and not intended for making definitive conclusions. Only a selected set of originally planned analyses will be performed and all data will be listed.

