4. ANALYSIS POPULATIONS

Table 1 Analysis Populations

Population	Definition / Criteria	Analyses Evaluated
Intent to Treat Exposed Population (ITT- E)	Comprised of all randomized subjects who receive at least one dose of investigational product. Subjects will be assessed according to their randomized treatment, regardless of the treatment they receive.	Study Population and disposition
Safety	 Comprised of all randomized subjects who receive at least one dose of IP. This population will be based on the treatment the subject actually received. 	Safety
Influenza Positive Population (IPP)	Comprised of all subjects in the ITT-E population with influenza infection (positive influenza PCR or culture at any timepoint) confirmed by central lab testing.	Efficacy, Health Outcomes, Virology, Biomarker
PK	Comprised of all subjects who underwent blood PK sampling during the study and from whom one or more blood concentration is determined.	• PK
All Subjects Screened	Comprised of all subjects screened for inclusion in the study	Study Population

NOTES:

Please refer to Appendix 13: List of Data Displays which details the population to be used for each display being generated.

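### The SAP promises that all data will be listed, but its only listings of vital signs, discharge, ICU admission and readmission, and its post-baseline ventilation displays, cover centrally confirmed influenza cases only

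*SAP*

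**What the plan says.** The study stopped after 10 subjects were enrolled, and SAP 2.1 cuts the reporting back accordingly: "Only a selected set of originally planned analyses will be performed and all data will be listed". That sentence carries no population limit. SAP 8.1.1 then replaces most secondary efficacy summaries with listings of the underlying data: vital signs, ventilation, discharge, readmission and ICU stay.

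SAP Section 4 defines the populations:

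- IPP: "Comprised of all subjects in the ITT-E population with influenza infection (positive influenza PCR or culture at any timepoint) confirmed by central lab testing".
- Safety: "Comprised of all randomized subjects who receive at least one dose of IP".

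The same section refers the reader to "Appendix 13: List of Data Displays which details the population to be used for each display being generated". In that appendix (SAP 11.13.19), Listing 33 ("Listing of Vital Signs"), Listings 34-35 (mechanical ventilation and supplemental oxygen), Listing 36 (discharge), Listing 37 ("Listing of Subjects Who Were Admitted to Intensive Care Unit") and Listing 51 (readmission) all carry the IPP label. So does Table 2.3, the summary of post-baseline ventilation status.

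SAP Table 3, whose default population is ITT-E, marks both a table and a listing for ventilation and oxygenation status at baseline and at any time.

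**The concern.** With formal analysis abandoned, the listings are the main product of the report, and their value lies in covering every treated subject. A subject can be enrolled and dosed on a rapid or local test and then fail central confirmation. Under the display list as written, that subject's heart rate, blood pressure, temperature, respiratory rate, post-baseline ventilation, ICU admission, discharge and readmission would appear in no dedicated display. This is the first study of danirixin in hospitalized influenza, and Protocol 4.6.1 names worsening of virus-mediated disease among the risks to be watched. The clinical course of each dosed subject is what a reader would look for.

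**Working it through.** The SAP gives no figure to reproduce, so the check is a comparison of texts and a count of displays.

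**Can a dosed subject fall outside the IPP?** Yes. Inclusion criterion 7 (Protocol 5.1) accepts a positive rapid test or another local laboratory test. The IPP requires a positive PCR or culture at the central laboratory. The Safety and ITT-E populations require randomization and one dose only.

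**Which displays carry the data?** The 54 listings in SAP 11.13.18 and 11.13.19 divide by population as follows:

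| Population | Listings |
|---|---|
| ITT-E (Listing 14 is printed IIT-E) | 21 |
| Safety | 16 |
| IPP | 13 |
| All subjects screened | 2 |
| PK | 2 |
| Total | 54 |

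Four listings are dedicated to vital signs, discharge, ICU admission or readmission: 33, 36, 37 and 51. All 4 are on the IPP and none is on a wider population. The safety tables and figures (SAP 11.13.7 and 11.13.8) hold only adverse event and laboratory displays. SAP 8.2.3, on other safety analyses, covers only ECG. SAP 11.8.3 says vital signs will not be flagged for potential clinical importance, so no abnormal-value listing picks them up. Listing 33 is therefore the only listing of the raw vital signs.

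**Ventilation.** Table 3 plans an ITT-E table and listing covering any time point. Appendix 13 delivers less:

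| Display | Content | Population |
|---|---|---|
| Table 1.14 | Ventilation at baseline | ITT-E |
| Table 1.16 | Ventilation at baseline | IPP |
| Table 2.3 | Post-baseline ventilation | IPP |
| Listings 34-35 | Mechanical ventilation; supplemental oxygen | IPP |

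The SAP thus disagrees with itself on the population for post-baseline ventilation.

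**Does the SAP treat the IPP and ITT-E as identical?** Not consistently. The notes to Figures 2.1 and 2.2, both on the IPP, call for "10 lines for 10 subjects with different symbols representing event or censoring", which fits an IPP of all 10. But Tables 1.14 and 1.16 present the same summary on the two populations separately, Table 3 has a footnote marking some displays for both, and Listing 30 (chest X-ray, ITT-E) adds a column showing whether the subject is in the IPP.

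**Size.** The number of subjects outside the IPP is not given and could in principle be 0 to 10. Each would be 1/10 = 10% of those enrolled, assuming all 10 were dosed.

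**The case against.** The strongest reply is that the loss is hypothetical. The SAP was written after enrolment had ended, its figure notes expect 10 lines on an IPP figure, and a positive central result at any time point is enough to qualify. Listing 8 would at least name anyone excluded. This stands as a limit on the size of the point, but a programming note does not establish that the two populations coincide, and other displays allow for a difference.

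The second reply is that most of these items are not protocol safety endpoints. Protocol Section 3 places ICU stay, hospital stay, ventilation and the heart rate and blood pressure times under secondary clinical measures, and readmission under exploratory health outcomes. Protocol 9.3.1 makes the IPP the default for efficacy. This explains the labels. It does not reconcile them with the sentence in SAP 2.1, and the SAP lists biomarkers on ITT-E (Listings 42-45) although the biomarker analyses are on the IPP.

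The third reply is that serious events reach the Safety-population adverse event listings. They do so only in part. Under Protocol 12.4.1 and 12.4.2, expected progression of influenza is not an adverse event and so cannot be a serious one. An ICU transfer or readmission judged to be expected progression might never appear there.

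A reader might also infer a breach of the protocol, because Protocol 9.4.2 says "Laboratory data, vital signs and ECG data (absolute values and change from Baseline) will be summarized by visit and treatment group" and bases safety analyses on the Safety Population. The documents do not support that. The passage promises a summary, and SAP 2.1 openly drops planned analyses by keeping only a selected set.

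**Conclusion.** The inconsistency is real and minor. It lies within the SAP: the undertaking in 2.1 against the populations in Appendix 13 and, for ventilation, Table 3 against Appendix 13. Following the SAP as written would omit a dosed but centrally unconfirmed subject from the listings of vital signs, discharge, ICU admission and readmission, and from the post-baseline ventilation displays. If all 10 subjects are in the IPP, nothing is lost.

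Two further inferences go too far. One is that such a subject would have no ventilation record at all: Table 1.14 includes baseline ventilation on ITT-E, and Table 3 intends more. The other is to state the loss as a share of a treatment arm by applying 2:2:1 to 10 subjects. The actual arm sizes are not given, and Protocol 6.2 also describes minimization criteria, so no such percentage can be relied on.

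**What to change.** Before unblinding, relabel Listings 33-37 and 51 in Appendix 13 to the Safety or ITT-E population and add a column showing IPP membership, following Listing 30. For Listings 34-35 this also supplies the listing that Table 3 marks.

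Leave Tables 2.1-2.4, Listings 31-32 and Figures 2.1-2.2 on the IPP. They report efficacy, and the IPP is the protocol's efficacy population.

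The cost is a change of population label and one flag column in six listings. No new data are needed.
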